The proposed study will extend these results by including both sexes and extend our analysis of the relationship of baseline drinking to cope (DTC) and anxiety by adding baseline standardized questionnaires measuring trait anxiety (STAI), early life adversity (ACES), and a perceived stress scale (PSS) which in other settings was more predictive of health care utilization than stressful life event counts (Cohen, Kamarck et al. 1983). Women are expected to have a greater likelihood of elevated DTC, ACES, trait anxiety scores (Smith and Randall 2012) which will enrich our sample in subjects potentially more responsive to dutasteride vs. pbo. We will use separate randomizations for women vs. men and include dichotomized scores for DTC and *FKBP5* risk allele carrier status in our URN randomization to balance for these potential predictors of efficacy. This study may identify easy to score pre-treatment measures such as the CDMQ, ACES, STAI, PSS and genotype that could be clinically useful for making personalized treatment recommendations regarding use of dutasteride to reduce heavy drinking.

2.C. Experimental Approach / Research Plan

2.C.1. General Design: The study will be conducted in the UCHC Clinical Research Center (CRC) clinic. Random assignment to initial treatment group and double-blind conditions will be maintained throughout the study. The study consists of two 12-week phases (**Table 1**), the first being a 12-week parallel-groups comparison of dutasteride and pbo to evaluate the safety and efficacy of dutasteride 1 mg/day in reducing the likelihood of drinking and heavy drinking in a sample of treatment-seeking men and women with AUD. In the second 12-week phase, responders in phase 1 (defined as a ≥60% reduction in SD/wk for weeks 9-12 compared with screening) will continue on their initial medication assignment, while non-responder subjects treated with placebo will cross over to dutasteride, and non-responder subjects treated with dutasteride will cross over to naltrexone. This design maintains double blind conditions in both phases 1 and 2 and is innovative. This design will: i) promote retention and recruitment, as subjects who do not respond to treatment in phase 1 will cross-over to an active FDA approved medication for AUD, ii) provide two comparisons to examine dutasteride efficacy, a between-subjects

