comparison in phase 1 and a within-subjects test in phase 2 for patients treated with pbo in phase 1 and dutasteride in phase 2, iii) allow evaluation of whether reductions in drinking are maintained with ongoing treatment for phase 1 dutasteride responders, and iv) provide preliminary data on whether dutasteride non-responders show reductions in drinking when crossed over to naltrexone, an established medication for AUD with a different mechanism of action compared with dutasteride.

Three and six-month follow-up visits following the completion of the 24-week treatment phase will evaluate the durability of treatment effects, allow measurement of the degree to which dutasteride effects on 5AR inhibition have been reversed following 12- or 24-week exposures and to maintain contact with female participants to remind them of the importance of effective contraception for 6 months following treatment.

Table 1. Expected Patient Distribution for Phase 1 and 2.

Phase 1	Phase 1	Phase 1	Phase 2	Phase 2 Statistical contrasts
Treatment	Statistical	Expected Tx	Treatment	
	contrasts	response groups		
Dutasteride n=95 (grp A)	Between-subject contrasts using GLMM Dut vs. Pbo for DVs HDD/wk and SD/wk;.	Dut-R (wk 9-12 Response n=40) Dut-NR (wk 9- 12 Non-Response n=40)	Dut-R dutasteride Dut-NR naltrexone	Within-subject interrupted time series regression using mixed models. Dut-R: Is dut response maintained? Dut-NR: Do dut NRs respond to naltrexone?
	Moderating			
Pbo n=95 (grp B)	effects of genotype, baseline state vs. trait anxiety, perceived stress and interaction with FKBP5 genotype	Pbo-R (wk 9-12 Response n=16) Pbo-NR (wk 9- 12 Non-Response n=64)	Pbo-R pbo Pbo-NR dutasteride	Pbo-R: insufficient sample for statistical comparison. Pbo-NR: Do pbo NRs respond to Dut?

Phase 1 response ≥ 60% reduction SD/wk for wk 9-12 vs baseline (current study 49% response rate for dut vs. 20% pbo). dutasteride 1 mg/day; naltrexone 50 mg/day.

2.C.2. Patients: Drinkers who want to reduce or stop drinking will be recruited using advertisements in radio and print media, by posting/distributing recruitment materials in community settings, informational mailings to area clinicians and by referral from UConn Health medical and dental clinics in at our main campus in Farmington CT together with

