- 2.C.3.d. Medication Randomization and Drug Accountability: Urn randomization (Stout, Wirtz et al. 1994) will be used to assign subjects 1:1 to dutasteride or pbo for treatment phase 1, balancing for number of DSM5 AUD criteria (2-5 vs.>5), DTC relative to total motives score (0-25% vs. >25%), *FKBP5* genotype (CC vs. T-carrier), current smoking status, and use of medication for treatment of co-morbid psychiatric condition. Separate

randomizations will be done for women and men to ensure balance on these variables in both sex groups. At the end of phase 1, patients who have reduced drinks/week by at least 60% will continue for the second 12 wks on the originally randomized treatment taking 2 capsules per day. Subjects who have reduced drinks/wk by less than 60%, will be informed that they will be transitioning to an active study medication (either dutasteride or naltrexone), and will be interviewed to confirm they have not used opioid medication for 5 days prior which will be verified by urine testing, subjects testing positive for opioids will not be eligible for starting phase 2. For non-responder subjects in the phase 1 pbo arm, the pharmacy will begin dispensing 0.5 mg dutasteride capsules with instructions to take 1 capsule per day for 2 days, then 2 capsules daily for 12 weeks. For subjects in the initial dutasteride arm and reducing less than 60%, the pharmacy will dispense 25 mg naltrexone capsules with the same instructions of 1 capsule for days 1 and 2 followed by 2 capsules each day (50 mg naltrexone per day) to match the dutasteride capsule dosing. Medication vials including any unused medication will brought to each follow-up visit. Unused pill counts will be recorded by the study nurse at each bi-weekly visit and medication use recorded daily by patients on their drink log.

2.C.4. Study Visits:

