as to whether events occurred before age 6, between ages 6 and 17, above age 18 or within the past year. We previously reported an interaction of FKBP5 genotype and trauma measured with the TESI on drinking in a large college student sample (Lieberman, Armeli et al. 2016). Presence or absence of childhood trauma will be evaluated for main and interactive effects with FKBP5 genotype on predicting treatment outcomes; g) Adverse Child Experiences Scale (ACES) The ACES assesses early life stress in the form of childhood exposure to adverse experiences and a risky family environment (Felitti, Anda et al. 1998). This 17 item questionnaire probes childhood exposures including psychological abuse, physical abuse, sexual abuse, substance abuse within the family, mental illness within the family, violence toward mother, and criminal behavior in the household. Felitti et al. (Felitti, Anda et al. 1998) found that in a large sample of adults belonging to a HMO, more than half endorsed at least one category of childhood exposure. Individuals who had experienced four or more categories of childhood exposure had 4 to 12-fold increased risk for alcoholism, drug abuse, depression and risky sexual behavior. Scores for the ACES will be evaluated for main and interactive effects with the FKBP5 genotype on predicting treatment outcomes.

2.C.6.b.2. Areas assessed daily during the active treatment period: IVR will be used to collect daily subjective ratings of alcohol-related expectancies, craving, anxiety/tension, and self-efficacy to reduce drinking, as well as drinking amounts. To reduce subject burden for daily IVR in this 24-wk study, we will use IVR to capture daily data for the first 4 study weeks and the last 4 weeks of both phase 1 and phase 2. The IVR daily drinking data will be used together with bi-weekly drinking reports to determine treatment response (60% reduction in drinks/wk) during the last 4 weeks of phase 1 to inform treatment assignment for phase 2. Daily IVR reports will also enable us to address whether study medication moderates associations between daily mood, drinking motives, self-efficacy or daily events and drinking as has been reported using IVR methods for treatment with naltrexone and topiramate (Kranzler, Armeli et al. 2004, Armeli, Feinn et al. 2006). Moderation of relationships between daily mood reports and drinking by medication will be contrasted between baseline and end of phase 1 or 2.

Table 2: Schedule of Assessments

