For the phase 1 comparison of dutasteride and pbo over time, efficacy analyses will be performed using generalized linear mixed (GLMM) models implemented in SPSS. GLMM incorporates within subject correlation effects important in examination of repeated measures, can incorporate multiple covariates, interactions, random and fixed effects, nonnormal distributions, and is often recommended for designs such as proposed (Mallinckrodt C 2017). Medication group will be treated as a factor and treatment week as a continuous covariate. Sex, smoking status, treatment goal (stop vs. reduce drinking), and use of concurrent medication for co-morbid psychiatric conditions will also be examined as baseline between-subject covariates. Medication group, week, and the other covariates will be modeled as fixed effects, and the intercept will be modeled as random effects. For the outcome HDD/wk a binomial distribution with logit link will be used where the number of HDD during the week will be the numerator and number of observed days the denominator. For the outcome SD/wk a negative binomial distribution with log link will be used. An interaction term between medication group and the week term(s) will be used to evaluate whether the efficacy of dutasteride compared to pbo in reducing drinking varies over time. Interaction effects of sex and treatment condition will also be examined. Pretreatment drinking will be controlled using baseline TLFB drinking data as a covariate. The robustness of results will be evaluated by running the model under three different conditions: 1) modified intention to treat using all available outcome information from subjects with at least 1 post-randomization visit, 2) data from 12-week per protocol completers, and 3) multiple imputation using 10 imputed data sets with weekly drinking and baseline covariates thought predictive of the outcomes or missingness included in the imputation phase.

For aim 2, phase 2 outcomes, the within-subjects analysis will compare drinking during phase 1 against phase 2 for three groups: a) patients responsive to dutasteride in phase 1 and continuing on dutasteride for an additional 12-weeks in phase 2, to examine whether the response is maintained with continued treatment; b) phase 1 non-responders crossed over from pbo in phase 1 to dutasteride in phase 2 to provide a second contrast using an A-B design of the efficacy of dutasteride compared with pbo; and c) phase 1

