dutasteride arm non-responders switched to naltrexone to determine whether naltrexone is effective in reducing drinking in dutasteride non-responders. An interrupted time series regression using mixed models will be used (Wagner, Soumerai et al. 2002, mallinckrodt and Lipkovich 2017), where in addition to a variable for week an indicator variable for phase, a second weekly variable that is sequentially coded beginning at phase 2 and the interaction of the two variables will be included in the model. The phase indicator variable will measure change when entering phase 2 and the second weekly variable will measure change in trajectory deviating from phase 1. In addition, a restricted period analysis focusing on the average of the last 4 weeks of phase 1 compared to average of the last 4 weeks of phase 2 will be conducted. This may be more sensitive if the first few weeks of each phase show limited initial response, which would dilute the effects for phase and the interaction for the interrupted regression model. For the first group, dutasteride responders, a non-inferiority test will be used where the non-inferior margin will be 20% above the drinking levels during phase 1. For the latter two groups of non-responders a superiority test will be used.

For aim 3, analysis of drinking outcomes will be repeated including baseline measures of DTC, trait anxiety, perceived stress, adverse child event count and genotype for the *FKBP5* rs1360780 SNP (CC vs. T-carrier) as additional between-subject factors together with the 2- and 3-way interactions of medication condition with DTC, SAI, PSS or ACES measures and *FKBP5* genotype. We will include both Blacks and Caucasians in the pharmacogenetics analysis as our prior study showed similar interactions of *FKBP5* genotype with life stress on drinking measures in both Black and Caucasian college students (Lieberman, Armeli et al. 2016).

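### Aim 2 reads uncontrolled before-after changes in selected non-responders as efficacy of dutasteride against placebo and of naltrexone

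*Combined protocol and SAP*

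**What the plan says.** Section 2.C.1 (item ii) says the design will "provide two comparisons to examine dutasteride efficacy, a between-subjects" one from the randomised phase, the second being the change within people who move from placebo to dutasteride. Section 2.C.9.a.2 repeats the claim for placebo non-responders switched to dutasteride: the analysis is "to provide a second contrast using an A-B design of the efficacy of dutasteride compared with pbo". For dutasteride non-responders the purpose is "to determine whether naltrexone is effective in reducing drinking in dutasteride non-responders".

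Who enters these groups depends on the end of phase 1. Section 2.C.1 continues on their initial drug the "responders in phase 1 (defined as a ≥60% reduction in SD/wk for weeks 9-12 compared with screening"; the rest cross over. Section 2.C.6.b.2 uses the daily telephone reports together with the biweekly reports "to determine treatment response (60% reduction in drinks/wk) during the last 4 weeks of phase 1 to inform treatment assignment for phase 2". Section 2.C.3.d adds: "Subjects who have reduced drinks/wk by less than 60%, will be informed that they will be transitioning to an active study medication".

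Two analyses are planned. The first is an interrupted time series mixed model over both phases: "The phase indicator variable will measure change when entering phase 2", and a second weekly variable captures the change in slope. The other compares the mean of the last four weeks of phase 1 with the mean of the last four weeks of phase 2. Both non-responder groups get a superiority test. Section 2.C.9.b gives 90% power for a medium effect with 64 placebo non-responders and a within-subjects t-test.

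Other places are more cautious. Section 2.B describes the placebo crossover in exploratory terms, and item (iv) of 2.C.1 calls the naltrexone data preliminary.

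**The concern.** A comparison with placebo needs people on placebo at the same time who are otherwise alike. Phase 2 has none. In Table 1 all non-responders change drug. The only phase 2 placebo group is placebo responders (expected n=16), and Table 1 itself rules out a statistical comparison for that group because it is too small.

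Three things other than the drug can move drinking at the switch:

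- **Regression to the mean.** People are selected because weeks 9-12 were high relative to screening. Those weeks are the whole reference in the restricted-period test, and they are the end of the phase 1 segment in the time series.
- **Expectancy.** Participants learn at the switch that the next drug is active.
- **Time.** Drinking may drift up or down under continued biweekly counselling.

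Followed as written, a positive phase 2 test could be reported as a second demonstration of dutasteride efficacy against placebo, or as proof that naltrexone works in dutasteride non-responders.

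**Working it through.** **1. The plan's own power figure.** Inputs from 2.C.9.b: n=64, within-subjects t-test. The size of a medium effect is not restated for Aim 2b; Aim 1 uses d=0.4 and α=0.05. Assuming these values and a two-sided test:

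- Normal approximation: Φ(0.4×√64 − 1.96) = Φ(1.24) = 89%.
- Noncentral t with 63 df: 88.3%. Exactly 90% needs d of about 0.41.

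The stated 90% is therefore reproduced. It is power to detect a mean within-person change from any cause, not a dutasteride-placebo difference.

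**2. Direction of the selection effect.** Take standardised drinking in weeks 9-12 and 21-24 as bivariate normal with correlation ρ and no drug effect. Select the upper fraction p on weeks 9-12. The expected fall is (1−ρ)·λ, where λ = φ(c)/p and c is the cut-off. The preliminary response rates in Table 1 (20% placebo, 49% dutasteride) give p=0.80 and p=0.51, so λ = 0.35 and 0.78.

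At ρ=0.7 (assumed):

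- Placebo non-responders: fall 0.3×0.35 = 0.105 SD; divided by the SD of change, 0.75, this is 0.14. Chance of false superiority: Φ(0.14×8 − 1.96) = Φ(−0.84) = 20%.
- Dutasteride non-responders: fall 0.235 SD, paired effect 0.32. Simulated chance of false superiority with n=40: 51%.

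The fall is positive for any ρ below 1. The sizes are too high for this trial, because this model selects on the level of drinking whereas the protocol selects on the ratio to screening.

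**3. Size under the protocol's ratio rule.** None of the following inputs is in the documents unless stated. Log weekly drinking is a subject effect plus an AR(1) deviation (0.5); on-treatment SD 0.8, screening SD 0.4, screening correlation 0.5, screening median 45 drinks/wk. A responder has weeks 9-12 at or below 40% of screening (the plan's rule). Means are set to give 20% and 50% responders among 80 per arm, as in Table 1. Drugs are inert and there is no trend. The continuous model used 3000 runs; the daily-count model (gamma-Poisson, zero days allowed) used 800. The time series is approximated by per-subject segmented regression with a t-test on the phase term.

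False superiority (%), nominal 2.5%, at between-window correlation 0.5/0.7/0.8/0.9:

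| Test | Placebo to dutasteride, n about 64 | Dutasteride to naltrexone, n about 40 |
|---|---|---|
| SD/wk time series, continuous | 9/6/5/4 | 32/18/12/8 |
| SD/wk time series, daily count | 8/7/4/5 | 33/22/16/11 |
| SD/wk restricted period, continuous | 11/8/6/4 | 49/26/18/10 |
| SD/wk restricted period, daily count | 13/9/6/6 | 49/29/21/15 |
| HDD/wk time series, daily count | 24/18/11/9 | 62/46/32/19 |
| HDD/wk restricted period, daily count | 34/21/16/10 | 77/57/39/24 |

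Repeating the continuous SD/wk model at 0.5/0.7/0.9 gave restricted-period rates of 11/8/4% and 46/27/10%, and time-series rates of 9/6/4% and 34/20/9%. The HDD and drift runs were not repeated.

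The spurious paired effect on SD/wk is 0.03-0.10 (n=64) and 0.10-0.31 (n=40), against the 0.41 that n=64 detects with 90% power. Check at the upper ends: Φ(0.10×8 − 1.96) = Φ(−1.16) = 12%, and Φ(0.31×√40 − 1.96) = Φ(0.00) = 50%, in line with 13% and 49%.

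**4. Sensitivity.** Varying the SD over 0.5-1.0 and the screening correlation over 0.3-0.6 (daily count, 300 runs) widens the SD/wk restricted-period rates to 3-25% and 7-82%.

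**5. Drift unrelated to drug** (assumed; daily count, 300 runs; SD/wk):

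- 10% fall by weeks 21-24, restricted period: 30-41% (n=64) and 56-71% (n=40).
- 10% rise, restricted period: 0.3-2.3% and 2-23%.
- Fall over weeks 1-4, then flat, time series: 0.3-1.3% and 0.7-15%.

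**The case against.** The analysis is openly labelled within-subjects, 2.B and item (iv) of 2.C.1 use softer language, and Aim 1 carries the randomised efficacy test. Nothing says that phase 2 would override phase 1, so the harm depends on how results are reported. This limits the consequence, but it does not cure the wording: the softer passages conflict with the analysis section, and no passage limits the causal reading or mentions regression to the mean.

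The time series does adjust for each group's own linear phase 1 trend. That is a real advantage over a plain pre-post mean. It cannot remove selection on the last four phase 1 weeks, nor an expectancy effect that coincides with the switch.

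The numbers are the weaker part. The simple normal model gives restricted-period rates of 9-30% and 20-75%, up to twice the ratio-rule figures or more, so size depends on the model. For the dutasteride switch the first-listed analysis gives only 4-9% on SD/wk, and with an early fall then flat it drops below nominal; that result is about 1 to 4 hits in 300 runs, too few for precision. The HDD runs used five or more drinks for everyone, whereas section 2.C.2.b sets a lower daily limit for women. The slope-change term and the interaction were not simulated in these runs. All of this stands, and it is why only the direction of the selection component is treated as firm.

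A text-only remedy also leaves the inflated tests in place. That is acceptable if the plan says that they support no efficacy claim.

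**Conclusion.** The concern holds. The phase 2 non-responder analyses are single-group before-after comparisons in people selected on part of their own reference period. They show neither the efficacy of dutasteride against placebo nor the effectiveness of naltrexone. This conclusion follows from the design and needs no simulation. Selection by itself favours an apparent fall whenever the between-window correlation is below 1. Under the stated assumptions the effect on SD/wk is modest for the dutasteride switch and larger for naltrexone. The net bias could go either way once drift is added, which is a further reason not to read the change as a drug effect. The plan should be corrected, but the randomised phase 1 comparison is not touched.

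**What to change.** Change the wording in three sections.

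- **2.C.1, item (ii):** replace the claim of two efficacy comparisons with *one randomised comparison of dutasteride efficacy (phase 1) and, in phase 2, an uncontrolled, exploratory before-after change in placebo non-responders switched to dutasteride*.
- **2.C.9.a.2, placebo non-responders:** replace "to provide a second contrast using an A-B design of the efficacy of dutasteride compared with pbo" with *to describe an uncontrolled, exploratory before-after change after the switch to dutasteride*.
- **2.C.9.a.2, dutasteride non-responders:** replace "to determine whether naltrexone is effective in reducing drinking in dutasteride non-responders" with *to describe an uncontrolled, exploratory before-after change after the switch to naltrexone*.
- **2.C.9.a.2, after the sentence on superiority tests:** add *These superiority tests will not support an efficacy claim.* Naming regression to the mean from selection on weeks 9-12 as a reason would be a harmless addition.
- **2.C.9.b, Aim 2b:** add that the 90% power is for an uncontrolled pre-post change and not for a dutasteride-versus-placebo effect.

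The phase 2 questions in Table 1 and the Aim 2 hypotheses can be aligned at the same time. The cost is text only: no new data, visit or analysis. The downside is a weaker phase 2 claim, with the efficacy conclusion for dutasteride resting on phase 1 alone.

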
For the majority non-smoker group (n=111) there was a significant interaction of medication group by treatment week (HDD/wk F=6.2, df=1,1183, p=0.013; and SD/wk F=4.7, df=1,1183, p=0.031) **Figure 1**, such that dutasteride treated subjects reduced drinking over time more than placebo subjects. During the last 4 weeks of the 12-week treatment period, the proportion of subjects with a \geq 60% reduction in SD/wk compared with screening (which represents a clinically meaningful reduction from a group average of 48 SDs/wk to less than 20) was significantly greater for the dutasteride vs. the pbo group [49% vs. 20%; χ^2 =8.3, p=0.004; OR=3.8 (95% Cl=1.5-9.8)]. Additionally, among the 91 per protocol completers, during the last month of treatment 33% of subjects in the dutasteride arm had no heavy drinking and 27% no hazardous drinking (no HDDs and no more than 14 SD/wk) compared with 11% and 2% of pbo- treated subjects respectively [no HDD days [χ^2 =6.7, p=0.01; OR = 4.1, NNT=5]; and no hazardous drinking [χ^2 =11.1, p=0.001; OR = 16.4, NNT=4]. The additional analysis described below focuses on the group of 111 non-smokers.

[figure not shown]
Figure 1. Heavy Drinking Days per week (left) and Standard Drinks per week (right) for pbo vs dutasteride treated nonsmokers (mean±SEM).

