2.C.3.a. Dutasteride is FDA approved to treat prostatic hypertrophy and is a competitive and specific inhibitor of both type I and type II steroid 5α-reductase enzymes with which it forms a stable enzyme complex with very slow dissociation. In humans, type I 5AR is present in the brain, liver, adrenal gland, and adipose tissue and is responsible for onethird of circulating DHT. Type II 5AR is present in the liver and prostate, and is responsible for two-thirds of circulating DHT. For studies of alcohol use, inhibition of type I 5AR may be of particular importance, as type I 5AR, but not type II enzyme, is present in the adult brain (Lephart, Lund et al. 2001) where local generation of neuroactive steroids is thought to occur in addition to peripherally generated neuroactive steroids. The dutasteride dose of 1 mg/day proposed for this study is expected to achieve a >90% inhibition of peripheral type II 5AR and a 60% inhibition of type 1 5AR by 4 weeks for a total reduction in DHT of ≅ 80% by 4 wks based on pharmacokinetic models (Gisleskog, Hermann et al. 1998) and consistent with our observed 80% reduction in 3α-adiol glucuronide at 6 wks in our recently completed initial study in men using this dose. Dutasteride will be purchased commercially and over encapsulated using opaque capsules by the UConn Health Research Pharmacy Service. Pbo will be formulated to match the active medication. Subjects will take one 0.5 mg capsule of dutasteride or matching pbo during the first

treatment visit (baseline study visit 2) and at home on day 2 followed by two capsules daily for either 12 or 24 weeks (depending on treatment response). Similarly, subjects transitioning from placebo or dutasteride based on phase 1 non-response will be given one capsule of medication (dutasteride 0.5 mg or naltrexone 25 mg) during their first phase 2 study visit and day 2 of phase 2 followed by two capsules daily for 12 weeks.

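### For dutasteride responders, the time series step and slope-change terms cannot test maintenance, and the plan does not tie the Aim 2a non-inferiority test to one level contrast with one reference period

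*Combined protocol and SAP*

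**What the plan says.** Aim 2A asks whether dutasteride responders, defined by a fall of at least 60% in weeks 9-12, keep that reduction during phase 2. For all three aim 2 groups, section 2.C.9.a.2 states: "An interrupted time series regression using mixed models will be used". It then interprets the terms: "The phase indicator variable will measure change when entering phase 2", and "the second weekly variable will measure change in trajectory deviating from phase 1". Table 1 gives no other method for the responder question: "Within-subject interrupted time series regression using mixed models. Dut-R: Is dut response maintained".

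The same section has two further elements:

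- It adds "a restricted period analysis focusing on the average of the last 4 weeks of phase 1" against the matching average for phase 2. The reason given is that a slow initial response could dilute the time series effects.
- It gives responders a non-inferiority test, with a margin 20% above their phase 1 drinking. Section 2.C.9.b puts the margin at 0.67 HDD/wk or 5 SD/wk, for 40 responders, 80% power and alpha 0.05.

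The plan does not say which model term or contrast carries the non-inferiority test, which of the two analyses leads, or whether the phase 1 reference is all 12 weeks or weeks 9-12.

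**The concern.** Maintenance means no further change. The time series asks something else: whether phase 2 departs from the line fitted to phase 1. Responders are selected for having fallen a long way by weeks 9-12, so their phase 1 line probably slopes down. The earlier trial points the same way for dutasteride-treated non-smokers as a whole: "dutasteride treated subjects reduced drinking over time more than placebo subjects". For such a group the model's comparator is continued decline, and holding steady registers as worsening.

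The non-inferiority rule could avoid this, but its reference is open. A whole-phase reference includes the early, heavier-drinking weeks and so errs in the opposite direction. One permitted reading can signal deterioration where there is none, and another can pass a real relapse. The choice between them could be made after the data are seen.

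**Working it through.** **Algebra.** Take log(mean SD/wk) = a + b·week + c·phase + d·week2, where week2 counts from the start of phase 2 and is 0 before it. The log link is stated for SD/wk in phase 1 and is assumed here for phase 2. The listed interaction is left out because it is redundant: phase × week2 equals week2, and phase × week equals 12·phase + week2.

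- The phase 2 slope is b + d. If phase 2 is flat, b + d = 0, so d = -b. Any falling phase 1 (b < 0) gives d > 0.
- If phase 2 is held at level L, the step is c = log(L) - (a + 12b), the gap between L and the phase 1 line at week 12. It is zero for a steady log-linear fall held at its week 12 level, and positive when the fall levels off.

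**Inputs.** Section 2.B.2 describes a fall from a group average of 48 SD/wk to below 20. The 60% rule gives a ceiling of 0.4 × 48 = 19.2. The decline shapes are assumptions: 17 + 31·exp(-t/τ) for weeks t = 1 to 12, and a steady log-linear fall 48·(17/48)^(t/12). Each is then held exactly at its week 12 level to week 24. The two slowest curves average 19.3 and 19.5 in weeks 9-12, marginally above the ceiling.

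**Results, no noise.** The last column is the rise over weeks 9-12 that a whole-phase reference would allow: 1.2 × (mean of weeks 1-12) / (mean of weeks 9-12) - 1.

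| Decline | Mean wk 1-12 | Mean wk 9-12 | Slope change per week | Step ratio | Wk 21-24 / wk 9-12 | Rise allowed |
|---|---|---|---|---|---|---|
| τ = 0.5 wk | 17.40 | 17.00 | +1.0% | 1.03 | 1.00 | 23% |
| τ = 1 | 18.50 | 17.00 | +3.0% | 1.09 | 1.00 | 31% |
| τ = 2 | 20.97 | 17.19 | +5.9% | 1.15 | 0.99 | 46% |
| τ = 3 | 23.41 | 18.00 | +7.1% | 1.13 | 0.98 | 56% |
| τ = 4 | 25.64 | 19.33 | +7.3% | 1.10 | 0.96 | 59% |
| Log-linear | 28.59 | 19.45 | +9.0% | 1.00 | 0.87 | 76% |

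For the last row, 1.2 × 28.59 / 19.45 - 1 = 0.76. The total phase 2 slope (b + d) is 0 in every row.

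**Simulation.** This used 300 trials per curve, 40 patients, overdispersed counts and one-sided 5% tests. Curves fell from 36 to 16 SD/wk and then stayed flat; the variances are assumed. The slope-change term was significantly positive in 100% of trials for each of three falling curves and in 7% for a curve flat throughout. When phase 2 drinking was instead set 20% above the level reached in phase 1, non-inferiority against the whole-phase mean was still declared in 97-100% of trials (two curves tried).

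**The plan's own margin.** The figure of 5 SD/wk cannot be reproduced because no SD of change is given. With n = 40, 80% power and one-sided 0.05, it implies SD = 5·√40 / (1.645 + 0.842) = 12.7 SD/wk. It equals 20% only at a phase 1 level of 5 / 0.20 = 25 SD/wk. At 19.2 SD/wk, 20% is 3.84.

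**The case against.** The strongest reply is that the plan never makes the time series coefficients the decision rule for responders. It sets a non-inferiority test on drinking level, sizes it as a level increase, and already includes the weeks 9-12 against weeks 21-24 comparison. Being listed first does not make the time series primary. The same model yields the total phase 2 slope, which is zero under maintenance. Nor does a 60% fall from screening fix when the fall happened: if most of it comes in the first week or two, the slope change is only +1% to +3% per week. The section 2.B.2 trend describes all dutasteride-treated non-smokers, not responders, and the inhibition figure at 4 weeks in section 2.C.3.a concerns enzyme activity, not drinking.

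All of that stands, and it rules out a stronger reading. A reader might infer that Aim 2a will get the wrong answer, or might set the maintained level (two to three times the projected one by weeks 21-24 on the slower curves) against the 20% margin. The documents do not support either. The margin is defined on the phase 1 drinking level, not on the projection, and a level contrast does not report a loss when response is held (ratios 0.87-1.00 above).

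The reply does not remove the gap. Table 1 still ties maintenance to the time series, the interpreted terms are the step and the deviation in slope, and the level test has neither a named contrast nor a defined reference.

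**Conclusion.** The point holds in limited form. For responders, the slope-change term is positive under perfect maintenance whenever phase 1 drinking fell, and the step is positive too if the fall levelled off. Neither can support a conclusion about maintenance. The sign follows from algebra. The size, +1% to +9% per week, rests on the assumed curves and on how early the fall occurs.

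Aim 2a is exposed to error in both directions because the non-inferiority test is not tied to a contrast or a reference. Read as all 12 weeks, the reference is too lenient: about 23-76% above the weeks 9-12 level would fit within the margin, again on assumed curves. The randomised phase 1 comparison is unaffected.

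**What to change.** In section 2.C.9.a.2 and Table 1:

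1. Name the level contrast of weeks 21-24 against weeks 9-12 as the sole Aim 2a maintenance test, with weeks 9-12 as the reference for the 20% margin (for example, upper confidence limit of the ratio below 1.20).
2. Keep the time series descriptive for responders. Bar its step and slope-change terms from the maintenance conclusion; the total phase 2 slope may be reported. The two non-responder groups can keep the planned model.
3. State that responders are selected on weeks 9-12, so some upward drift is expected and the test is slightly conservative.

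The change is to wording only; the comparison is already planned and needs no new data. Besides the conservatism, there is a cost in power that should be stated. At 19.2 SD/wk the margin is 3.84, not 5. With the implied SD of 12.7, power under exact maintenance is Φ(3.84·√40/12.7 - 1.645), about 60% rather than 80%. That assumes a one-sided test and that the implied SD applies to this contrast. Section 2.C.9.b should give the SD used and reconcile the 20% and 5 SD/wk forms of the margin.
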